## Funder

None required

This protocol describes the assessment of measurements of angulation of the C-spine and provides information about procedures for entering participants. Every care was taken in its drafting, but corrections or amendments may be necessary. These will be circulated to investigators in the study. Problems relating to this study should be referred, in the first instance, to the Chief Investigator.

This study will adhere to the principles outlined in the UK Policy Frame Work for Health and Social Care Research. It will be conducted in compliance with the protocol, the Data Protection Act and other regulatory requirements as appropriate.

## Glossary of Abbreviations

C-spine	Cervical spine
MRI	Magnetic resolution imaging

**Keywords:** Comfort, measurements of angulation, MRI, spinal collar

## Study Summary

**Title** Comparison of measurements of the cervical spine in adults with and without immobilisation.

**Design** Controlled study without randomisation

**Aims** Determine if a young persons neck is the same shape as an older persons neck.  
Determine if a spinal collar alters the shape of the neck.  
Assess the level of discomfort in a spinal collar

**Outcome measures** Measurements of angulation of the C-spine on MRI scan  
Visual analogue scale for pain

**Population** Adults aged 18yrs – 30yrs and 70yrs and over.

**Eligibility** Persons who have no discomfort in the neck, no known medical condition and no previous injury affecting the neck or spine.

**Duration** 12 months

## 1. Introduction

### 1.1 Background

Through our own experience we have noticed the external shape of an older persons neck appears to be different to that of a younger person with older patients necks being angled towards the floor rather than upright even when they do not have an obvious curvature (kyphosis) to the rest of their spine. We have also noticed that older patients do not tolerate wearing a spinal collar as well as younger ones and therefore would like to assess the level of comfort when wearing a spinal collar in healthy volunteers. This will help us to assess whether older patients do not tolerate the spinal collar as well as younger patients due to pain from their injury or from the collar itself.

### 1.2 Rationale for current study

Limited research has been performed in this area; our proposed study will assess the difference in the shape of the neck when comparing the younger population to the older population. Additionally we would like to assess whether the shape of the neck changes when wearing a spinal collar and how comfortable the device is to wear.

## 2. Study Objectives

- a) Determine if a young persons neck is the same shape as an older persons neck.
- b) Determine if a spinal collar alters the shape of the neck.
- c) Assess the level of discomfort in a spinal collar

## 3. Study design

Non-randomised controlled study

### 3.1 Participant identification

Recruitment of volunteers will take place via poster advertisements displayed in public areas at St Mary's Hospital, Paddington. Interested persons will be able to contact the research team via the email address written on the poster. Following initiation of contact with the research team potential participants will be sent a patient information leaflet, which will include necessary requirements for inclusion and exclusion criteria.

### 3.2 Methodology

This is a prospective study aiming to assess the shape of the neck in adults. In addition the study will look at the shape of the neck in a spinal collar and the comfort while wearing a spinal collar.

Age of participants to be recruited: 18yrs and over - 30yrs and 70yrs and over. Adult research participants will be recruited from the general public via poster. Interested persons will be asked to contact the research team via email. Patient information leaflets and an MRI safety questionnaire will be accessible via email correspondence.

On making contact with the research team interested persons will have the opportunity to ask any questions prior to agreeing to the study with a minimum of 24hrs between having the opportunity to discuss participation with the research team and agreeing to the study.

Participants must consent to the GP being contacted with the scan report to ensure appropriate record keeping especially in the event of an incidental finding.

Participants will be required to attend the hospital for half a day on a specified weekend day.

On arrival participants will be asked to fill in a validated questionnaire (Visual Analogue Score) about the level of discomfort in their neck.

Participants will need to fill in a safety questionnaire prior to the neck scan and change into a hospital gown for the scan. Participants will undergo a neck scan, which requires the participant to spend approximately 5 minutes lying flat in the scanner.

The participant will then have a spinal collar fitted by an expert (equivalent to that fitted in standard clinical practice) and spend one hour wearing the collar.

Following one hour wearing the spinal collar the participants will be asked to repeat the same questionnaire regarding comfort and a second neck scan with participants wearing the spinal collar will be performed (requires the participant to spend approximately 5 minutes lying flat in the scanner).

Scans will be reported by a medical expert (Radiologist) and reports sent to the GP. The anonymised scans will also be analysed by expert scientists at Imperial College for measurements of angulation.

### **3.3 Study outcome measures**

Measurements of angulation of the neck taken from MRI scans.

Visual Analogue Scale Scoring (pain severity score)

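### Objective (c) is discomfort in a spinal collar, but its only outcome is labelled a pain score, and no item is described that asks about the collar itself

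*Combined protocol and SAP*

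**What the plan says.** Section 2 and the Study Summary give the third aim as "Assess the level of discomfort in a spinal collar". Section 1.2 puts the same interest as "how comfortable the device is to wear", and section 1.1 says the team "would like to assess the level of comfort when wearing a spinal collar in healthy volunteers".

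One outcome can serve this aim. The Study Summary lists it as "Visual analogue scale for pain" and section 3.3 as "Visual Analogue Scale Scoring (pain severity score").

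Section 3.2 says how it is collected. On arrival, before any collar is fitted, participants complete a validated visual analogue questionnaire "about the level of discomfort in their neck". After one hour in the collar, "the participants will be asked to repeat the same questionnaire regarding comfort". The item wording, the anchors, the direction of the scale and the body site on the form are not stated anywhere. Section 6 says there is no routine follow-up.

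**The concern.** Pain, neck discomfort and comfort are related but different things to rate, and discomfort in a collar is different again. A person may find a collar hot, tight or restrictive without calling that pain. A person may also be uncomfortable at the chin, jaw or shoulders and not in the neck. If the form asks only about pain, or only about the neck, such a person can truthfully score zero.

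Any loss of this kind runs in one direction: it makes the collar look more comfortable than participants found it. A larger sample does not remove it. Nor can it be repaired afterwards, because participants attend once, for half a day. As the text stands, a reader of the results could not tell whether the reported score is neck pain, neck discomfort or collar comfort.

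**Working it through.** No arithmetic applies. The question is which construct is measured, and the documents give no figure on this point to reproduce. The check is to set the descriptions side by side.

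| Place | What is to be assessed or rated | Site or source |
|---|---|---|
| Study Summary (aims) and section 2 | discomfort | in the collar |
| Section 1.2 | comfort | of the device |
| Section 1.1 | comfort, and whether pain comes from the injury or the collar | wearing the collar |
| Study Summary (outcomes) and section 3.3 | pain severity | not stated |
| Section 3.2, on arrival | discomfort | neck |
| Section 3.2, after one hour | comfort, on the same form | not restated |

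**Step 1: how many instruments?** One. Section 3.2 says the second administration repeats the first form, and section 3.3 lists a single VAS. So one instrument carries three labels (pain, neck discomfort, comfort), while the objective uses a fourth description (discomfort in the collar).

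**Step 2: what follows under each reading?**
- *The form is a pain score, as the summary and 3.3 say.* Collar discomfort that is not pain has no place to be recorded.
- *The form asks about neck discomfort, as 3.2 says for arrival.* Discomfort in the neck that is not pain is covered. Discomfort from the collar elsewhere is not.

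**Step 3: could the repeat be about the collar?** The same form is completed on arrival, when no collar is worn. A question used unchanged on both occasions can hardly be specific to the collar. So the word comfort in the second description does not establish that the collar itself is rated.

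**Step 4: can the gap be filled later?** No later contact is planned for this purpose. The only follow-up contact described is a clinic appointment offered after an adverse incidental scan finding.

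**Step 5: can the loss be sized?** No. That would need the form's wording and the share of participants whose collar discomfort is not pain or not in the neck. The documents give neither.

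**The case against.** The strongest reply is that the form may already ask the right thing. Section 3.2 is the only account of what participants are actually asked, and it says discomfort. The pain label in 3.3 may simply name a familiar type of scale, and comfort and discomfort may be loose wording for one continuum. This stands as far as it goes: inconsistent labelling is proven and a measurement loss is not. It does not close the gap, because 3.2 still locates the discomfort in the neck while the objective concerns the collar.

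A second reply is that pain is what the study is about, since section 1.1 asks whether older patients tolerate the collar poorly "due to pain from their injury or from the collar itself". Pain is indeed relevant, and the paired score should stay. But the same paragraph also seeks the level of comfort, and poor tolerance need not be painful, so a pain score does not cover objective (c) by itself.

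A third reply is that section 4.3 mentions a visual analogue score or questionnaire, which might hint at a second form. That may equally be the MRI safety questionnaire, and no separate comfort instrument is described.

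A reader might go further and infer that the study will miss non-pain discomfort, that its answer on collar discomfort is biased by some definite amount, or that the scale changes direction between the two administrations. The documents support none of these. The form is not reproduced, 3.2 says the same form is used twice, and any figure for the bias would rest wholly on assumed inputs.

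**Conclusion.** The point holds as a mismatch between objective (c) and its only outcome, together with inconsistent labelling of that outcome. Following the stated outcome could under-record what the objective asks about, and any shortfall would favour the collar. Its size is unknown and may be zero. The conclusion rests on two assumptions: that the VAS is the only comfort or pain instrument, as the text indicates, and that the form's site is the neck, as 3.2 says for arrival. This is a cheap improvement to make before data collection. It does not show that the study fails.

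**What to change.** 1. Check the validated form. State its construct, exact item wording, anchors, direction and body site, and use that description consistently in the Study Summary, section 3.2 and section 3.3. If the form asks about pain, call it pain. Renaming it discomfort would not change what it measures and would misdescribe it.

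2. Keep the paired VAS on arrival and after one hour. Add one VAS item at the end of the hour, anchored from *no discomfort from wearing the collar* to *worst imaginable discomfort from wearing the collar*. Report it by age group alongside the paired VAS for objective (c).

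**Cost.** Wording changes in three places and one extra line for participants at a visit they already attend. The added item is not part of the validated questionnaire and has no pre-collar value, so it supplements the paired VAS and cannot replace it. If the validated form turns out to ask only about pain, the added item will be the only record of other collar discomfort.

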## **4. Participant Entry**

### **4.1 Pre-registration evaluations**

Demographic values (age, sex, ethnicity).

### **4.2 Inclusion criteria**

1. Persons aged 18yrs and over to those aged 30yrs
2. Persons aged 70yrs and over
3. Ability to give informed consent to participate in the study

### **4.3 Exclusion criteria**

1. Persons under 18yrs of age and those aged 31yrs -69yrs
2. Persons who lack capacity to consent for entry into the study
3. Persons who are unable to complete the visual analogue score or questionnaire due to co-existent severe hearing and visual loss. Severe hearing impairment will be defined as unable to hear the researcher with hearing aids if required. Severe visual

impairment will be defined as being unable to read the patient information sheet even with visual aids.

4. Persons unable to understand the information leaflet in English.
5. Those with current neck pain, known previous C-spine injury or known medical condition affecting the spine.
6. Persons who do not pass the safety questionnaire to undergo an MRI scan
7. Persons who are knowingly unable to tolerate an MRI scan due to claustrophobia
8. Persons who are unable to transfer to the scanner table independently
9. Persons unable to lie flat and still for 10 minutes
10. Persons who do not give consent to the GP being informed of scan results.

#### **4.4 Withdrawal criteria**

1. Loss of capacity during the study will result in automatic suspension from the study until capacity is regained.
2. Participants may choose to withdraw from the study at any time. Withdrawal will not affect the clinical care delivered.

### **5. Adverse Events**

The study does not involve any invasive intervention, spinal collars and MRI scans are used in usual clinical practice therefore we do not anticipate any adverse events as a result of participation in the study.

### **6. Assessment and follow up**

All MRI scan reports will be sent to the participants General Practitioner (GP). In the event of any adverse incidental findings a clinic appointment will be offered at St Mary's Hospital, Paddington. There will be no routine follow up for participants.

### **7. Statistics and Data Analysis**

Data analysis will be via standard parametric statistical analysis. Data will be kept for a maximum of 10 years following completion of the study.

## **8. Regulatory Issues**

### **8.1 Ethics approval**

The Study Coordination Centre has obtained approval from the xxx Research Ethics Committee (REC) and Health Regulator Authority (HRA). The study must also receive confirmation of capacity and capability from each participating NHS Trust before accepting participants into the study or any research activity is carried out. The study will be conducted in accordance with the recommendations for physicians involved in research on human subjects adopted by the 18th World Medical Assembly, Helsinki 1964 and later revisions.

### **8.2 Consent**

Participants must have capacity to consent. Consent to enter the study must be sought from each participant only after a full explanation has been given, an information leaflet offered and at least 24 hours allowed for consideration. Signed participant consent should be obtained. Participants must consent to their GP being

sent a copy of their MRI scan result. The right of the person to refuse to participate without giving reasons must be respected. All participants are free to withdraw at any time from the study.

Consent will be taken by a physician who holds a Good Clinical Practice (GCP) qualification and is qualified to assess capacity for consent. Should it come to the attention of the clinical or research team (research team form part of the clinical team) that a patient has lost capacity the participant will be suspended from the study.

### **8.3 Confidentiality**

The Chief Investigator will preserve the confidentiality of participants taking part in the fulfil transparency requirements under the General Data Protection Regulation for health and care research

### **8.4 Indemnity**

Imperial College Healthcare NHS Trust holds standard NHS Hospital Indemnity and insurance cover with NHS Litigation Authority for NHS Trusts in England, which apply to this study.

### **8.5 Sponsor**

Imperial College Healthcare NHS Trust will act as the main Sponsor for this study.

### **8.6 Funding**

No external funding has been applied for. Participants will not receive any payment for participation. Participants will be offered a picture of their neck imaging.

### **8.7 Audits**

The study may be subject to inspection and audit by Imperial College London under their remit as sponsor and other regulatory bodies to ensure adherence to GCP and the NHS Research Governance Framework for Health and Social Care

## **9. Study Management**

The day-to-day management of the study will be co-ordinated through [name] and the Research team.

## **10. Publication Policy**

Completed research will be submitted to a peer-reviewed journal for publication

